This is an investigator-initiated, single-center, randomized, placebo-controlled, double-blind study. The intervention duration is 10 weeks. The follow-up period is 24 weeks. The recruitment period is 30 months. The total study duration will be 3 years.

(ii) Methods

Primary outcome

The primary outcome is the change of DAS28-CRP at 4 weeks comparing prednisolone group and placebo group.

Secondary outcomes

- 1) Changes of RA disease activity at week-8, week-12 and week 24 comparing the 2 groups.
- 2) Changes of RA disease activity at different time points within the 2 groups.
- 3) Disability at different time points comparing the 2 groups.
- 4) Proportion of patients with adverse events comparing the 2 groups.
- 5) Independent predictors of RA disease control in all participants.

Treatment and clinical evaluations

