To monitor the possible side effect of prednisolone and other medications, complete blood count, liver function test and renal function test will be performed at screening, week 4, week 8 and week 12 and week 24. Body mass index, blood pressure, blood sugar and lipid profile will be checked at baseline, week 4, week 8, week 12 and week 24. Chest x-rays will be obtained at screening and when clinically indicated. Hepatitis status and electrocardiogram will be done at screening. The treating physicians will record all adverse events (AEs) and, if necessary, make treatment adjustments in accordance with the protocol. Serious AEs (SAEs) are defined as the occurrence of life-threatening condition or death, a significant or permanent disability, a malignancy, hospitalization or prolongation of hospitalization, a congenital abnormality, or a birth defect. AEs of special interest (AESI) will also be collected which include any AE leading to drug discontinuation, MACE (myocardial infarction, cerebrovascular or peripheral arterial vascular event), newly occurring hypertension/diabetes/infection/cataract/glaucoma and fragility fracture.

iii) Subjects (with justification on the sample size)

Consecutive RA patients attending the rheumatology clinics of PWH will be screened for eligibility. The inclusion criteria are: 1) ≥ 18 year-old, 2) fulfilment of the 2010 ACR/EULAR classification criteria of RA, 3) never use of any DMARDs for RA, 4) disease activity score 28-C-reactive protein (DAS28-CRP) > 3.2 , and 5) Chinese subjects only. The exclusion criteria are: 1) pregnancy or premenopausal women planning pregnancy, 2) functional status class IV (limited in ability to perform usual self-care, vocational, and avocational activities), 3) use of systemic GC in recent one month, and 4) contraindications to prednisolone. A total of 112 patients who meet the criteria will be included.

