A sample size determination was conducted for the primary outcome measurement, the difference in the change of DAS28-CRP at 4 weeks comparing the 2 groups, using Power Analysis and Sample Size Software (PASS version 11). From the published results of the GLORIA trial, the short-term (3 months) improvement in DAS28 in the prednisolone group and placebo group was 1.36 ± 1.14 (baseline 4.40 ± 1.04) and 0.73 ± 1.21 (baseline 4.46 ± 0.99) respectively (21). In our pilot study mentioned above, the improvement in mean DAS28 was -1.4 ± 1.3 post-treatment. Therefore, more conservatively, we expect the difference of the change of DAS28-CRP at 4 weeks to be 0.6 comparing the prednisolone and placebo group. At least 49 patients will be required in each group to achieve a statistical power of 0.8 with a two-sided α of 0.05. With an estimated dropout rate of 15%, a total sample size of 112 would be required.

The study will be submitted to The Joint Chinese University of Hong Kong – New Territories East Cluster Clinical Research Ethics Committee and the Central Institutional Research Board of the Hospital Authority for approval. It will also be submitted to the clinicaltrials.gov for registration. Written informed consent will be obtained from all participants prior to any of the trial procedure. The study will be conducted according to the Declaration of Helsinki and ICH-GCP guidelines.

(iv) Data processing and analysis

Patients who discontinue treatment or violate treatment protocol will be excluded from the analysis (per-protocol analysis). Missing data are assumed missing at random and will be treated using a multiple imputation method. Descriptive statistics will be used to present the baseline demographic and clinical variables included frequencies, means with standard

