deviations and median with interquartile range. T-test or Mann-Whitney U test and Chi-square test or fisher exact test will be used to evaluate the differences in clinical variables between the prednisolone and the placebo group at baseline, depending on the data distribution. The primary outcome measurement, the difference in the change of DAS28-CRP at 4 weeks comparing the 2 groups, will be analyzed by T-test. Clinical variables which are significantly different between the 2 groups in the univariate analyses and are biologically plausible (eg. age, sex, disease duration, disease activity or treatment) will be adjusted in the multivariate logistic regression model to confirm the prednisolone treatment effect. The secondary outcomes on disease activity at week 8, week 12 and week 24 or disability in terms of HAQ at different time points will be compared likewise. The within group changes of these measurements before and after treatment will be examined using paired t-test or Wilcoxon signed-rank test. To look for the changes across study period across 2 groups, the repeated ANOVA test will be performed. To address the secondary outcome of comparison of proportion of patients with AE in the 2 groups, Chi-square test will be performed and cross-checked by generalized estimating equation (GEE) analysis. Sensitivity analysis using an intention-to-treat approach including all randomized patients will be done. A 2-tailed probability value of $p<0.05$ is considered statistically significant. Calculation will be performed using IBM SPSS Statistics Version 24 (IBM, Armonk, NY, USA).

(v) Potential pitfalls and contingency plans

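### The primary week-4 test is an unadjusted t-test on change in DAS28-CRP; it is valid, but leaves the baseline score held for every patient unused, and adjusting for it costs almost nothing

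*Protocol*

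**What the plan says.** Section d(ii) of the protocol defines the endpoint: "The primary outcome is the change of DAS28-CRP at 4 weeks comparing prednisolone group and placebo group". Section d(iv) fixes the test: "The primary outcome measurement, the difference in the change of DAS28-CRP at 4 weeks comparing the 2 groups, will be analyzed by T-test". Disease activity at weeks 8, 12 and 24, and HAQ, "will be compared likewise".

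Adjustment appears only in the sentence after the t-test, and only for some variables: "Clinical variables which are significantly different between the 2 groups in the univariate analyses and are biologically plausible". Disease activity is one of the examples given. These variables "will be adjusted in the multivariate logistic regression model to confirm the prednisolone treatment effect".

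Section d(iii) sets the entry threshold, "disease activity score 28-C-reactive protein (DAS28-CRP) > 3.2", so each randomised patient has a baseline value. The randomisation text in section d(ii) gives permuted blocks of 4 and names no stratification factor.

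**The concern.** A change score analysed by t-test subtracts the whole baseline value, which amounts to fixing the slope of week-4 on baseline DAS28-CRP at 1. If the true slope differs from 1, two things follow. Residual variance is larger than it need be, which widens the confidence interval. Any chance difference between the arms at baseline also leaks into the estimated treatment effect.

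The conditional step in section d(iv) does not cure this. It admits baseline disease activity only if the arms differ significantly, whereas the precision gain needs no imbalance and imbalances short of significance still move the estimate. It names a logistic model, which does not fit a continuous change. It is also a confirmation that follows the primary test and does not replace it. The choice of test is stated in the protocol, so it is not a detail left to a later analysis plan.

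**Working it through.** **Inputs.** From section d(iii): target difference ("we expect the difference of the change of DAS28-CRP at 4 weeks to be 0.6"), two-sided 0.05, power 0.8, 49 per arm, 15% dropout, total 112, and the GLORIA three-month figures "1.36 ± 1.14 (baseline 4.40 ± 1.04) and 0.73 ± 1.21 (baseline 4.46 ± 0.99". From the introduction and section d(iii): pilot SDs of 0.7 at baseline, 1.6 at week 4 and 1.3 for the change. The protocol gives no follow-up SD for GLORIA, so s1 is an assumption and is varied from 1.0 to 1.6.

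**The plan's own figure.** Pooled change SD = √((1.14² + 1.21²)/2) = 1.176. Then n = 2(1.960 + 0.842)² × 1.176² / 0.6² = 60.3, so 61 per arm (62 by the t distribution), not 49. An SD of about 1.04 to 1.05 is needed to obtain 49. With 15% lost, 112 × 0.85 = 95.2, or about 48 evaluable per arm, which is used below.

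**Power of the t-test.** Noncentrality 0.6 / (1.176 × √(2/48)) = 2.50 on 94 df gives power 0.70.

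**ANCOVA.** Pooled baseline SD s0 = √((1.04² + 0.99²)/2) = 1.015.
- Correlation r = (s0² + s1² − 1.176²) / (2 s0 s1)
- Residual variance = s1²(1 − r²), and its ratio to 1.176²
- Slope b = r s1 / s0
- Shift of the unadjusted difference per 1-SE baseline imbalance = (1 − b) × 1.015 × √(2/48) = (1 − b) × 0.207

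Example, s1 = 1.2: r = (1.031 + 1.440 − 1.382) / 2.437 = 0.447; residual variance 1.440 × 0.800 = 1.152; ratio 1.152/1.382 = 0.83; b = 0.53; noncentrality 0.6 / (1.073 × 0.204) = 2.74 on 93 df; power 0.77; shift 0.472 × 0.207 = 0.10.

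| Assumed s1 | r | Variance ratio | Slope b | ANCOVA power (t-test 0.70) | 1-SE shift |
|---|---|---|---|---|---|
| 1.0 | 0.32 | 0.65 | 0.32 | 0.87 | 0.14 |
| 1.1 | 0.38 | 0.75 | 0.42 | 0.82 | 0.12 |
| 1.2 | 0.45 | 0.83 | 0.53 | 0.77 | 0.10 |
| 1.3 | 0.51 | 0.91 | 0.65 | 0.74 | 0.07 |
| 1.4 | 0.57 | 0.96 | 0.78 | 0.71 | 0.05 |
| 1.5 | 0.62 | 0.995 | 0.92 | 0.70 | 0.02 |
| 1.6 | 0.68 | 0.996 | 1.07 | 0.70 | −0.01 |

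The ANCOVA powers deduct one degree of freedom. Allowing also for estimating the slope (variance factor 1 + 1/92) takes off a further 0.3 to 0.5 points.

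**Pilot SDs.** r = (0.49 + 2.56 − 1.69) / (2 × 0.7 × 1.6) = 0.607; residual variance 2.56 × (1 − 0.369) = 1.616; ratio 1.616/1.69 = 0.96; power 0.61 to 0.63; b = 0.607 × 1.6/0.7 = 1.39. The shift is (1 − 1.39) × 0.7 × √(2/48) = −0.06, opposite in sign to most of the table.

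**Worst case.** If the slope is exactly 1, ANCOVA gains nothing and pays for one parameter. At 49 per arm and SD 1.049, power goes from 80.0% to 79.6%. At 48 per arm the loss is also under half a point.

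**What significance screening misses.** With baseline SD 1.015 and 48 per arm, the arms must differ by 1.99 × 0.207 = 0.41 units before the baseline test is significant. At s1 = 1.2, an imbalance just short of this shifts the estimate by 0.472 × 0.41 = 0.19, about 32% of the 0.6 target, without triggering adjustment.

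**Effect of the entry cut-off.** A simulation at 49 per arm, with baseline restricted to values above 3.2 (assumed SD 1.2 before truncation, equal week-4 SD), gave power of 61% for the t-test and 73% for ANCOVA at correlation 0.3, 73% and 80% at 0.5, and 90% and 93% at 0.7. Type I error was about 5% for both.

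**The case against.** The strongest reply is that nothing here is invalid. In a 1:1 randomised trial the t-test on change is unbiased and holds its type I error, and it matches both the declared endpoint and the quantity used for the sample size. Selection at DAS28-CRP above 3.2 produces regression to the mean in both arms alike. All of this stands. A reader might infer that the t-test is biased or inflates false positives; the documents do not support that.

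The size of the gain is also uncertain. The GLORIA SDs come from patients over 65 at three months, whereas this trial enrols DMARD-naive adults measured at four weeks. The only follow-up SD in the protocol is the pilot's 1.6; paired with the GLORIA SDs, it leaves almost no gain. That stands too, although seven patients cannot fix an SD. At 1.0, close to the GLORIA baseline SD, the gain is large.

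It is tempting to say that patients with higher baseline scores fall more. That needs a slope below 1. It follows from the GLORIA SDs for follow-up SDs up to 1.5, but the pilot SDs imply 1.39, the opposite direction. The documents do not settle it.

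The remaining reply is that disease activity is already among the candidates for adjustment. This does not answer the point, because that step depends on a significant imbalance and uses a logistic model.

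**Conclusion.** The point holds as a matter of precision and conditional bias. The protocol fixes an unadjusted primary test when a prognostic baseline value is available for everyone. At 48 per arm and a difference of 0.6, adjustment is worth anything from nothing to about 17 power points under the GLORIA SDs (0.70 to 0.87), depending on a follow-up SD that the documents do not give, and about 2 points under the pilot SDs. The downside is under half a point. A one-SE baseline imbalance moves the unadjusted estimate by up to about 0.14 units (24% of the target), with the sign depending on the slope; adjustment removes the linear part due to baseline DAS28-CRP and no other imbalance.

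A reader might also infer that the t-test causes the low starting power of 0.70, or that ANCOVA repairs the sample size. Neither follows. The 0.70 arises because 49 per arm does not follow from the cited change SDs. At the SD that 49 implies (1.049), the t-test has its planned 80%, and ANCOVA would still reach 89.9% with equal baseline and week-4 SDs and a correlation of 0.5. The sample-size basis needs its own correction. This change should be made, but the trial remains interpretable without it.

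**What to change.** Before unblinding, replace the t-test sentence in section d(iv) with wording to this effect: the primary outcome is analysed by linear regression (ANCOVA) of week-4 change in DAS28-CRP on treatment arm and baseline DAS28-CRP as a continuous covariate, reporting the adjusted mean difference, its 95% confidence interval and a two-sided p-value. Use the same model for disease activity at weeks 8, 12 and 24, and for HAQ with baseline HAQ as the covariate. Keep the t-test as a supporting analysis.

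Amend the following sentence as well, so that baseline disease activity is no longer adjusted conditionally, through significance screening in a logistic model, alongside an ANCOVA that already contains it.

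The cost is a few lines of text and one degree of freedom. No extra data, visits or patients are needed, and linear regression is available in the stated software.

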of low dose GC in terms of bone health has been emerging, where prednisolone ≤ 5 mg daily did not seem to be associated with reduced bone-mineral density in the recent Glucocorticoid-induced Osteoporosis in Patients With Chronic Inflammatory Rheumatic Diseases or Psoriasis (Rh-GIOP) study (27). The GLORIA trial also provide partial reassurance with regard to infection risk which is another most recognized adverse event of GC therapy. After 2 years of 5mg/day prednisolone, the proportion of patients (all aged ≥ 65) with at least one adverse event of special interest (serious or glucocorticoids-related) was increased by 24%, mostly due to non-severe infections. The result sets a benchmark for the upper limit of harm, and the risk in a less vulnerable population with lower dose and shorter duration of GC use is expected to be lower. All in all, “*does the concomitant use of GCs at very low doses increase therapeutic success without producing unacceptable side effects?*” is explicitly listed as one of the top research agenda in the latest EULAR RA management recommendations published in 2023 (6).

We believe the half-a-century long controversy regarding GC use in RA boils down to one final clinical question that whether very low dose GC is an effective and safe bridging therapy, as 1) chronic GC use is unanimously not advisable, 2) very low dose GC (prednisolone < 5 mg/day) appears to have no or minimal toxicity concern (28), and 3) prednisolone 4mg daily shows promising therapeutic effect in our preliminary study. Very low dose GC could be the universal add-on treatment for all RA patients initiating csDMARDs with an optimal benefit-risk ratio. To formally address this important clinical question, we plan to perform the first randomized controlled trial assessing the efficacy and safety of prednisolone 4 mg/day added to standard of care in patients with newly diagnosed RA. The results of our study are anticipated to be immediately implemental and can guide daily clinical practice.

c. Aims and Hypotheses to be Tested:

The aim of this study is to evaluate the efficacy of prednisolone 4mg/day added to standard of care in newly diagnosed RA patients with active disease. We hypothesise add-on prednisolone 4mg/day is efficacious compared to placebo in newly diagnosed RA patients with active disease.

d. Plan of Investigation:

(i) Study design

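### The introduction says the trial will address whether very low dose prednisolone is safe as well as effective, but the only stated safety comparison is a difference test that can seldom detect or exclude a moderate excess of harm

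*Protocol*

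**What the plan says.** The last paragraphs of section b(ii), Introduction, reduce the field to "one final clinical question that whether very low dose GC is an effective and safe bridging therapy" and announce a "trial assessing the efficacy and safety of prednisolone 4 mg/day added to standard of care in patients with newly diagnosed RA" that will formally address it. Section c is narrower: "The aim of this study is to evaluate the efficacy of prednisolone 4mg/day added to standard of care", and the hypothesis there is also about efficacy alone.

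In section d(ii), the proportion of patients with adverse events is the fourth of five secondary outcomes. Section d(iv) gives its analysis: "comparison of proportion of patients with AE in the 2 groups, Chi-square test will be performed and cross-checked by generalized estimating equation (GEE) analysis", with two-tailed p<0.05 as the criterion for significance. The protocol states no acceptable-harm limit and no power for safety. The sample size in section d(iii) rests on DAS28-CRP only.

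The introduction does supply a figure for harm. In an earlier trial of 5 mg/day over 2 years in patients aged 65 or more, the proportion with at least one adverse event of special interest (AESI) "was increased by 24%, mostly due to non-severe infections". The protocol comments: "The result sets a benchmark for the upper limit of harm", and adds that "the risk in a less vulnerable population with lower dose and shorter duration of GC use is expected to be lower".

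Section d(iv) also makes a per-protocol set the main analysis, leaving out patients who stop treatment, with intention-to-treat as a sensitivity analysis. Under Toxicity monitoring in section d(ii), any AE that leads to stopping the drug counts as an AESI. Section d(v) concedes that long-term safety cannot be examined, but says nothing about the precision of the short-term comparison.

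**The concern.** A test of no difference can reject equality when harm is large. Failing to reject says little unless the sample is large enough to make a relevant excess improbable. This sample was chosen for a continuous efficacy score, so the AE comparison may come out non-significant whether or not there is a moderate excess. Set beside an introduction that asks about safety and looks forward to a favourable benefit-risk balance, a bare p-value could be taken for more reassurance than it carries.

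The analysis set adds to this. If the per-protocol rule applies to the AE comparison, some patients who stopped because of an AE are dropped from the main safety result.

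**Working it through.** **Stated inputs.** 56 patients per arm, 1:1 (section d(ii)). Dropout 15% (section d(iii)), so 56 × 0.85 = 47.6, about 48 per arm. Two-sided alpha 0.05 (section d(iv)). A 24% increase as yardstick (section b(ii)). The plan gives no power figure for safety, so there is none to reproduce.

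**Assumed input.** The placebo AE proportion p is not in the documents, so a range is shown.

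**Step 1: relative reading.** The proportion on prednisolone is q = 1.24p. Power is the total binomial probability of all outcome pairs for which the uncorrected chi-square test gives p<0.05 (exact enumeration).

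| Placebo p | Prednisolone q | Excess, points | Power, 56 per arm | Power, 48 per arm |
|---|---|---|---|---|
| 30% | 37.2% | 7.2 | 13% | 12% |
| 40% | 49.6% | 9.6 | 17% | 16% |
| 50% | 62.0% | 12.0 | 24% | 22% |
| 60% | 74.4% | 14.4 | 38% | 33% |
| 70% | 86.8% | 16.8 | 60% | 53% |

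For placebo rates of 30-60%, p≥0.05 would occur in about 62-87% of trials at 56 per arm even if this excess were real. By the usual pooled formula, 80% power would need 675, 421, 268 and 166 patients per arm at 30%, 40%, 50% and 60%.

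**Step 2: percentage-point reading.** With q = p + 0.24 and p from 30% to 60%, exact power is 72-82% at 56 per arm and 67-77% at 48.

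**Step 3: detectable excess.** At 56 per arm and 50% on placebo, 80% power needs about 75% on prednisolone, an excess of about 25 points.

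**Step 4: what a null result would exclude.** With equal true proportions p, the 95% half-width of the risk difference is 1.96 × √(2p(1−p)/56).

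- p = 0.30 (0.60 differs little): 1.96 × √(0.42/56) = 0.170
- p = 0.50: 1.96 × √(0.50/56) = 0.185

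So the half-width is about 17 to 19 points, against an excess of 7.2 to 14.4 points in Step 1 for placebo rates of 30-60%. A perfectly balanced result would leave that excess inside the interval.

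**Step 5: the GEE cross-check.** As described, it is another comparison of the same two groups for a difference. It brings in no harm limit and does not change the above.

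**The case against.** The strongest reply is that this is an efficacy trial. Section c names efficacy only, AEs are a secondary outcome, and low power for such an outcome is ordinary. That stands: safety is not a confirmatory objective here. The point rests on the introduction's promise to address safety and on the method section d(iv) fixes for it.

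A reader might infer that the sponsor intends to read p≥0.05 as proof of safety. The protocol never says so. It sets p<0.05 as the mark of significance and is silent on what a non-significant AE result would mean.

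The yardstick is also borrowed. The 24% concerns AESI in patients aged 65 or over on 5 mg for 2 years. The tested endpoint here is any AE over 24 weeks in adults from 18. The protocol calls the figure an upper limit and expects less harm. It shows scale only; a smaller true excess would be harder still to detect.

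The result also depends on the placebo rate. At about 70%, power for the relative increase passes one half, and a non-significant result is no longer the likelier one. The percentage-point reading has the same effect, although a proportion increased by 24% reads more naturally as relative.

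Finally, one might claim that the introduction itself warns against this inference when it discusses cardiovascular events in the earlier 5 mg trial. It does not: that caution is about length of follow-up, not power.

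A confidence-interval method could be left to a statistical analysis plan. Here, though, the protocol itself fixes the test, the significance rule and the main analysis set, and itself raises the safety question.

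**Conclusion.** The point holds in a limited form. The stated difference test cannot show absence of harm. If the 24% is relative and the placebo AE rate is 30-60%, it has 13-38% power at 56 per arm (12-33% at 48), and a null result would not exclude that excess. A non-significant comparison would then usually neither detect nor exclude it. Both the placebo rate and the use of an AESI figure for any AE are assumptions.

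The documents do not support the stronger reading that the trial is designed to prove safety, or that p≥0.05 is likely whatever the assumptions. The mismatch lies between the introduction's question and a bare test with no interval, made worse by a main analysis set that leaves out patients who stop treatment. It should be corrected; the primary efficacy comparison is not affected.

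**What to change.** In section d(iv), make the safety result the risk difference and risk ratio, prednisolone versus placebo, each with a 95% confidence interval (Newcombe or Miettinen-Nurminen for the difference). Report them for patients with any AE and for patients with any AESI. Name the analysis set: all randomised patients who took study drug, in place of the per-protocol set. Keep the chi-square test as supporting only.

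In the introduction and in section d(v), state that short-term safety is described, that the trial is not sized to exclude a clinically relevant excess, and that p≥0.05 will not be read as evidence of safety.

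This costs analysis and wording only, with no added patients, visits or data. The downside is a weaker safety claim than the introduction now suggests.
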